Phase Ia: Safety study of a single bladder instillation of probiotic in adults. A subsample of healthy adults with neuropathic bladder who do not have urinary symptoms meeting the criteria for antibiotic treatment of urinary tract infection or initiation of the protocol will undergo a single intravesicular instillation of *Lactobacillus* to determine the tolerability of the instillation, safety of a single instillation, and whether the instilled *Lactobacillus* persists in the urine.

Study Design: We will recruit N=5 adult subjects with neuropathic bladder due to SCI or SB.

Clinical Setting: MedStar National Rehabilitation Hospital

The Impact of Self-Management with Probiotics on Urinary Symptoms and the Urine Microbiome in Individuals with Spinal Cord Injury and Spina Bifida Protocol

5/18/2017

Page 1 of 17

Target Enrollment: 5 subjects at least 18 years of age with SCI or SB and at least 1-year post-injury (if SCI).

Informed Consent: Consent will be obtained by the PI, Study Coordinator, or Research Assistant.

Inclusion Criteria: Inclusion criteria for safety study participants are: 1) age 18-50 years; 2) if SCI, at least 1-year duration; 3) neuropathic bladder, as determined by the attending physician; 4) utilizing intermittent catheterization for bladder management; and 5) community dwelling.

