Baseline Data Collection: At baseline, subjects who do not report urinary symptoms (see below) other than cloudy or foul-smelling urine will complete the validated USQ-NB. Urine will be collected for urinalysis and urine culture (see below for methods of urine collection), however urinalysis results will be used for post hoc data collection only and not inclusion/exclusion in keeping with the recommendations of the IDSA.

Intervention: Eligible patients will undergo 1 *Lactobacillus* (Culturelle GG, 20 Billion live organisms) instillation by study personnel at the study site. For the intravesicular *Lactobacillus* instillation, the contents of 1 *Lactobacillus* capsule will be mixed into 45 cc sterile 0.9% saline (adult bladder volume is 450cc, so this amount represents 10% of adult bladder volume). After mixing, study personnel will draw up the 45 cc of the liquid *Lactobacillus* mixture into a 60cc catheter tip syringe and instill via the intermittent catheter. Participants will be observed in the clinic for 30 minutes after instillation to assure that no adverse reactions occur.

Post-Intervention Follow-Up: After completion of the one *Lactobacillus* instillation and 30 minute observation period, participants will be asked to monitor for any symptoms using the USQ-NB daily for one week. They will be instructed to contact study personnel in the event of any urinary symptoms. They will then return to the clinic 5-10 days after instillation for repeat urinalysis and urine culture.

Phase 1b: Safety study of single bladder instillation probiotic in children with SB or SCI. After Phase 1a is complete, accumulated safety data (inclusive of adverse events and laboratory results)

The Impact of Self-Management with Probiotics on Urinary Symptoms and the Urine Microbiome in Individuals with Spinal Cord Injury and Spina Bifida Protocol

5/18/2017

Page 2 of 17

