will be presented to the DSMB. Phase 1b will be initiated only after review and approval of the Phase 1a safety data by the DSMB. Once approval demonstrates that a single dose of intravesicular *Lactobacillus* has been determined to be safe in adults, the same safety study will be repeated in children. A subsample of healthy children with neuropathic bladder due to SB who do not have urinary symptoms meeting the criteria for antibiotic treatment or initiation of the protocol will undergo a single intravesicular instillation of *Lactobacillus* to determine the tolerability of the instillation, safety of a single instillation, and whether the instilled *Lactobacillus* persists in the urine.

Study Design: We will recruit N=5 children with neuropathic bladder due to SB or SCI.

Clinical Setting: MedStar National Rehabilitation Hospital and Children's National Medical Center.

Target Enrollment: 5 subjects at least 6 years of age with SB or SCI, at least 1-year post-injury (if SCI).

Informed Consent: Consent and assent will be obtained by the PI, Study Coordinator, or Research Assistant.

Inclusion Criteria: Inclusion criteria for safety study participants are: 1) age ≥ 6 years; 2) if SCI, at least 1-year duration; 3) neuropathic bladder, as determined by the attending physician; 4) utilizing intermittent catheterization for bladder management; and 5) community dwelling.

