If participants instill *Lactobacillus* at any time during the intervention phase, and after *Lactobacillus* instillation reports a UTI as an Adverse Event (AE) we will request their urinalysis and urine culture results to attempt to determine if *Lactobacillus* might have been the cause of the UTI. If determined necessary by the PI, Co-PI and/or DSMB other AEs reported could require retrieval of medical records.

Phase III: Pilot Study of Multiple (up to 2) *Lactobacillus* Bladder Instillations

We will recruit 30 persons in whom we will collect urine up to 18 timepoints (up to monthly for the first year when not experiencing symptoms, up to two times when subject experience urinary symptoms, follow-up after either *Lactobacillus* treatment or antibiotics, and three (3) months into the six (6) months follow-up) in order to **estimate the strength of the associations between successful implementation of the probiotic self-management program and urinary symptoms, bladder inflammation, and the urine microbiome.** We will conduct an 18-month study in which each participant will serve as his/her own control through 3 phases of study: 6-months usual care (baseline), 6-months probiotic intervention, and 6-months follow-up
Study Design: We will recruit N=30 subjects with neuropathic bladder who will contribute urine samples for analyses.

Clinical Setting: MedStar National Rehabilitation Hospital and Children's National Medical Center.

Target Enrollment: 30 adult subjects at least 1-year post-injury and 18 years of age with SCI/MS or at least 18 years of age with SB

Recruitment Strategy: SCI/MS and SB subjects will be enrolled with assistance from United Spinal Association. Additionally, we will query the MedStar National Rehabilitation Hospital inpatient service, the 40+ MedStar National Rehabilitation Network outpatient sites, various MedStar Network databases, and the CNMC Spina Bifida database. Databases will be queried for participants who meet the eligibility criteria and have already provided HIPAA authorization and consent to be contacted for future research. Announcements and IRB-approved flyers will be posted on the United Spinal Association and study websites and at participating institutions.

Informed Consent: Consent will be obtained by the PI, Study Coordinator, or Research Assistant. All project staff are currently CITI certified and have passed all requirements for HIPAA certifications.

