For the intravesicular *Lactobacillus* instillation, the contents of 1 *Lactobacillus* capsule will be mixed into 45 cc sterile 0.9% saline (adult bladder volume is 450cc, so this amount represents 10% of adult bladder volume). After mixing, study personnel will draw up the 45 cc of the liquid *Lactobacillus* mixture into a 60cc catheter tip syringe and instill via the intermittent catheter. For children volume is based on age (see table on page 4 of protocol). Study participant will recheck symptoms after 24 hrs (valid range 22-30 hrs) following the SMP_{PRO} protocol and either complete another *Lactobacillus* instillation or seek medical attention. If symptoms still persist 4 hrs after second instillation, study participants should seek medical attention.

Post-Intervention Follow-Up:

After completion of the 6-month patient-initiated self-management protocol intervention period, participants will monitor symptoms weekly using the USQ-NB. At the end of follow-up, we will obtain another urine sample from all participants.

Measurements:

In addition to the measurements described in Phase II the following measurements will occur for phase III;

Urine Acquisition: A 50-100 ml urine sample will be collected from each subject for (1) urinalysis and cultivation, and (2) urine microbiome by SMRT sequencing. Urine will be collected from a new, unused intermittent catheter.

Urine Preparation: Collected urine will be immediately placed at 4°C. Within 6 hours, samples will be taken to CNMC for sequencing preparation. At CNMC, urine samples will be centrifuged at 4°C, 5,000 x g for 20 minutes. The supernatant will be aliquoted in 2 ml cryotubes and frozen at -20°C. 10ml PBS will be added to the pellet with the remaining supernatant and then centrifuged (5,000xg) at 4°C for 20 minutes. The pellets and aspirated PBS wash solution will be stored at -20°C. Pellets will later be transferred for DNA isolation and SMRT sequencing.

Urinalysis: Urine samples will be assessed utilizing standard clinical microbiology semiquantitative chemical testing using commercial disposable test strips for glucose, bilirubin, ketone, specific gravity, blood pH, protein, urobilinogen, nitrite, and leukocyte esterase. After centrifuging for 5 minutes, microscopic examination for and quantification of WBCs, RBCs, epithelial cells, yeast, bacteria, *Trichomonas vaginalis*, sperm cells, mucous filaments and crystals will be performed using standard microbial techniques.

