Urine Culture: Standard urine culture microbiology will be performed. A measured amount is inoculated to each of the appropriate media. A calibrated loop designed to deliver a known volume (0.01 ml per loopful) of urine is used. The sample will be mixed thoroughly and the top of the container removed. A calibrated wire-inoculating loop is flamed and allowed to cool without coming in contact with any surface. The sterile loop is inserted into the urine sample vertically and urine is allowed to adhere to the loop. The loopful of urine is inoculated over MacConkey agar plates using standard methods. Similarly, a second loopful is collected and inoculated on a blood agar plate. The plates are incubated aerobically at 35-37°C for at least 24 hours. The colonies and colony forming units (CFUs) are counted by multiplying with 100 (since 0.01 ml loop was used).

SMRT Sequencing Methods: Thawed urine samples will be clarified by low-speed centrifugation and bacterial genomic DNA will be isolated from pelleted bacteria using a DNeasy tissue extraction kit (Qiagen) according to manufacturer's instruction. 16S rRNA genes will be amplified using universal primers 28F 5'-AGAGTTTGATCMTGGCTCAG-3' and 1492R 5'-ACCTTGTTACGACTT-3'. These primers will amplify sequences that correspond to the sequence between positions 27 and 1492 in *E. coli* 16S rRNA and produce amplification products of approximately 1500 bp. These amplification products will be used for sequencing template

The Impact of Self-Management with Probiotics on Urinary Symptoms and the Urine Microbiome in Individuals with Spinal Cord Injury and Spina Bifida Protocol

5/18/2017

Page 9 of 17

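### Phase Ia and 1b aim to learn whether the instilled Lactobacillus persists in urine, but no Phase I urine test is described as identifying Lactobacillus, so the aim cannot be answered in either direction

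*Combined protocol and SAP*

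**What the plan says.** **The aim.** The Phase Ia introduction lists three things to be determined: tolerability, safety of a single instillation, and "whether the instilled *Lactobacillus* persists in the urine". Phase 1b states the same three, and its text says that "the same safety study will be repeated in children". For size, Phase Ia says "We will recruit N=5 adult subjects with neuropathic bladder due to SCI or SB"; Phase 1b recruits five children.

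**The Phase I tests.** Under Baseline Data Collection: "Urine will be collected for urinalysis and urine culture (see below for methods of urine collection". Under Post-Intervention Follow-Up: "They will then return to the clinic 5-10 days after instillation for repeat urinalysis and urine culture". Phase 1b takes both steps from Phase Ia by reference. Sequencing is not named in either phase.

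**The laboratory methods.** These come under Phase III, Measurements, introduced by "In addition to the measurements described in Phase II the following measurements will occur for phase III". The Urine Culture paragraph says "The loopful of urine is inoculated over MacConkey agar plates using standard methods". A second 0.01 ml loop goes on blood agar, incubation is aerobic for 24 hours or longer, and colonies are counted and multiplied by 100. The Urinalysis paragraph includes microscopy that quantifies bacteria. SMRT sequencing of 16S rRNA genes is in the same Phase III block.

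**Attribution in Phase II.** If a participant reports a UTI as an adverse event after an instillation, the Medical Information section says "we will request their urinalysis and urine culture results to attempt to determine if" Lactobacillus might have been the cause. The Phase II Study Design otherwise uses no urinalysis or culture.

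**The concern.** A persistence aim needs a test that can recognise the instilled organism and a rule for calling it persistent. Phase I describes neither. A total colony count reports how much grew, not what grew.

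At stake is one of the three stated Phase I aims, in all 10 participants. These are the only people who receive a single instillation, without symptoms, under clinic observation. If the plan is followed as written, the Phase I report could make a statement about persistence that its data cannot carry.

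Phase II has a related but smaller gap. Attribution of a UTI to the product rests on outside culture results, and the provider letter, as described, notifies the provider of the study and asks for results to be shared. It does not ask the laboratory to look for or report Lactobacillus.

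**Working it through.** There is no stated sample-size or power figure to reproduce, because Phase I has no such calculation. The check sets the tests against the aim and then asks how much a negative result could say.

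**1. Can any Phase I test identify Lactobacillus?**

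| Test | Named for Phase I? | Read-out described | Identifies the organism? |
|---|---|---|---|
| Urinalysis | Yes | Bacteria quantified by microscopy | No |
| Urine culture | Yes (method given under Phase III) | Colonies × 100, two media | No step described |
| 16S SMRT sequencing | No (Phase III) | Taxonomic classification | Yes |

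**2. The culture read-out.** The plan's multiplier checks: 1 / 0.01 ml = 100, so one colony is 100 CFU/ml. If a plate fully supported the organism, zero colonies would exclude, at 95%, concentrations above -ln(0.05) / 0.01 = 299.6, or about 300 CFU/ml. That bound does not hold if the organism grows poorly on the plate, and the documents give no recovery rate.

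**3. What a negative says.** Let s be the probability that the culture detects Lactobacillus in a participant who still carries it. This is an assumption, so a range is shown. Treating the five adults as independent, and supposing all five still carry the organism, P(0 of 5 positive) = (1 - s)^5.

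| s (assumed) | P(0 of 5 positive, all five carrying) |
|---|---|
| 0 | 1.00 |
| 0.05 | 0.77 |
| 0.20 | 0.33 |
| 0.45 | 0.05 |
| 0.50 | 0.03 |

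The one-sided 95% upper bound on the true persistence proportion after 0 of 5 solves (1 - p·s)^5 = 0.05, so p = (1 - 0.05^(1/5)) / s = 0.451 / s, capped at 1. It is 45% at s = 1, 90% at s = 0.5, and no bound at all once s is 0.45 or lower.

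**4. What a positive says.** The SMRT Sequencing Methods section reports about 189 bacterial species in preliminary samples from patients with neuropathic bladder. Phase I also admits people whose urine is cloudy or foul-smelling. Growth at 5-10 days is therefore possible with no Lactobacillus present, and an unidentified count cannot be assigned to the product.

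**5. Size of the remedy.** 10 participants × 2 urines = 20 samples. The plan's formula for sequencing capacity gives 189 × 1 × 87 / 30,000 = 0.55, which supports its statement that one SMRT cell per sample suffices. That makes 20 cells.

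**The case against.** **The culture method belongs to Phase III.** Using that block's introduction to keep sequencing out of Phase I, while borrowing the culture method from the same block, looks selective. It is true that applying the method to Phase I is an inference: the Phase Ia pointer to text below covers only how urine is collected. But sequencing is left out here because the Phase I sections do not name it, whereas they do name culture. If the culture paragraph does not apply, Phase I has no described culture method, and the aim is no better served.

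**Standard culture may include identification.** A clinical laboratory might name what it grows, and the culture paragraph refers to appropriate media. The protocol describes no such step and no persistence criterion. One sentence would settle it.

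**A negative might carry some information.** A reader might infer that a negative culture says nothing at all. The documents do not support that. It would require zero recovery on both media, yet a blood agar plate is included, incubation is a minimum of 24 hours, and no recovery rate is given. What stands is that a negative is weak by an unknown amount. The argument above does not depend on the selectivity of MacConkey agar.

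**Persistence drives no decision.** This is fair. It feeds no gate, primary outcome or power calculation, and even a perfect assay with 0 of 5 positive leaves an upper bound of 45%. That limits the weight of the point but does not supply the missing assay.

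**Conclusion.** The point holds. As written, Phase I cannot establish whether the instilled Lactobacillus persists: a zero count does not show clearance and a positive count does not show persistence. This covers all Phase I persistence evidence, from 5 adults and 5 children. It rests on two things: that the Phase I culture is either the one described under Phase III or undescribed, and that no unstated identification step is performed. The probabilities above depend on an assumed s and are illustrations. Improving this is worthwhile and cheap; it does not undermine the tolerability or safety aims.

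Three stronger conclusions might be inferred but lack support:

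- **That the DSMB would be shown a false finding of non-persistence.** The five report sections in the Data and Safety Monitoring Plan contain no persistence item. The Phase 1b gate is a review of safety data, and nothing turns a zero count into a persistence conclusion.
- **That Phase III UTIs caused by the product would be misattributed.** Phase III plans metagenomic samples at up to two symptomatic occurrences and after treatment, with an additional sample when a participant seeks care. A taxon-level test is available within those limits.
- **That Phase II attribution is biased in a known direction.** The outside laboratories' methods are not in the documents, and no rule says that a negative culture means unrelated. What can be said is that no study assay backs up the outside result.

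**What to change.** **Phase I: choose one of three.**

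1. Send the paired baseline and 5-10 day urines through the 16S pipeline already described for Phase III, extending its urine preparation and storage steps to these samples.
2. Add to the Phase I culture a medium that supports Lactobacillus, with identification of the organism grown.
3. Remove persistence from the Phase Ia and 1b aims.

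Under option 1 or 2, state the criterion in advance: persistence means Lactobacillus detected at follow-up relative to that participant's own baseline, so that organisms already present are not credited to the product. Report the result as a count out of five with an exact interval, for adults and children separately. Also state in the Phase I sections which culture method applies.

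**Phase II.** Add a sentence to the provider letter asking the laboratory to look for and report Lactobacillus. Where that was not done, record attribution to the product as not assessable.

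**Cost.** About 20 extra sequencing runs or plates on urine already collected, the handling that goes with them, and one sentence in the letter. No additional patient procedure is needed. Option 3 costs only a text change, at the price of giving up the question.

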H1. Compared with usual management, self-management of urinary symptoms with probiotics will reduce the frequency, severity and impact of urinary symptoms and UTIs (PRIMARY OUTCOMES). The goal of aim 2 is to assess the effect of *Lactobacillus* supplementation on the frequency, severity and impact of urinary symptoms and UTIs. This aim can be evaluated with all 100 participants in the SMP pilot study. We expect to find a significant difference in these primary outcomes between our three experimental timeframes (6 months prior to intervention, 6 months of SMP_{PRO} intervention, and 6 month follow-up period). Frequency of UTI will be defined as the number of verified UTIs occurring during the timeframe. Urinary symptoms will be assessed using the USQ-NB where frequency of symptoms, degree of severity, and impact on the individual, will be considered.

We will estimate the average number of symptoms on the USQ-NB endorsed (irrespective of frequency, severity and impact) across the weeks during that time frame, for each participant. Thus, each participant will have a continuous outcome (average number of USQ-NB items endorsed). We will also compute the number of verified UTIs experienced by each participant. These two outcomes are the primary outcomes for our study and analysis; they depend solely on the face validity of the USQ-NB, and on clinically verified UTIs, and so will not be affected by a failure to find or establish formal measurement properties for the USQ-NB, should any occur. They will also be less subject to any variability in participant perceptions of frequency, severity or impact, which can complicate analytic assumptions and limit power and interpretability of change that might be perceived. We will describe these features of the sample over time but will not conduct inference tests on these ratings.

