We propose linear mixed-effects modeling to explore the effect of introduction to/use of the SMP_{PRO} on the number of USQ-NB symptoms (averaged over the entire time frame) and the incidence of UTIs. Each model will include gender as a fixed effect, and time (baseline; SMP_{PRO} use; post-SMP_{PRO} observation) as the explanatory variable, and random effects for intercept (subject) only. This method allows for missing data and the inclusion of covariates where appropriate; however we plan post-hoc analyses of the modeling in order to pinpoint potential interaction effects (e.g., between age or sex and time). The focus of the analyses is to determine whether (irrespective of individual starting values or specific slopes) mean USQ-NB item endorsement and UTI counts go down in the SMP_{PRO} time frame relative to the baseline values (generally negative associations in each regression between the outcome and time) and whether these values stay flat (zero slope), continue to decrease (negative slope) or increase (positive slope) during the post-SMP_{PRO} follow up.

Power calculation: We plan to use mixed effects regression modeling for the most precision in our estimated effects of the SMP_{PRO} on the USQ-NB symptom rate and UTI rate. However, it is difficult to predict the exact form of the final models since our understanding of the USQ-NB symptom makeup, and the univariate associations between gender or age (or any other of the demographic variables we will collect) and these two outcomes. Therefore, for the most conservative estimates, we use the most basic analytic method to estimate the worst-case scenario power calculation, a t-test. In this pair of primary outcomes, alpha is set at 0.025 for each power calculation (and for each inference test). We will have data from 100 participants; however, to protect against a possible 20% drop out rate over the course of the 18-month study, we will recruit 120 persons for this arm, hoping for a final N of 100. If we observe an average of 25 items on the USQ-NB endorsed over the baseline period, then with alpha = 0.025 we would have 81% power to detect a reduction in this average number of items endorsed as low as five

The Impact of Self-Management with Probiotics on Urinary Symptoms and the Urine Microbiome in Individuals with Spinal Cord Injury and Spina Bifida Protocol
5/18/2017

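### The UTI co-primary is a raw count per six-month timeframe with no term for time observed and no rule for part-observed periods, so dropout can shift it in either direction

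*Combined protocol and SAP*

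**What the plan says.** All of this is in the combined protocol and SAP, mostly under H1.

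- Outcome: "Frequency of UTI will be defined as the number of verified UTIs occurring during the timeframe". The count is computed per participant and not divided by time observed.
- Model: linear mixed-effects, with gender as a fixed effect and time (baseline, self-management period, follow-up) "as the explanatory variable, and random effects for intercept (subject) only".
- Question asked: whether "mean USQ-NB item endorsement and UTI counts go down in the" self-management (SMP) period relative to baseline.
- Rate language: the power paragraph refers to effects "on the USQ-NB symptom rate and UTI rate", and the model paragraph speaks of incidence. Neither defines a person-time denominator.
- Missing data: "This method allows for missing data and the inclusion of covariates where appropriate". There is no rule for a timeframe observed only in part.
- Dropout: recruitment is set at 120 to protect against "a possible 20% drop out rate over the course of the 18-month study", "hoping for a final N of 100". The timing of dropout is not given.
- Alternative model: Poisson may be used if normality fails. No offset is mentioned.

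The other co-primary is an average of endorsed items across weeks, so it does not fall merely because fewer weeks are observed.

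**The concern.** A random-intercept model copes with an absent record. It cannot tell that a recorded count covers two months rather than six. If someone leaves during the SMP or follow-up period and the short count is kept, it is read as a low six-month count, which is the direction H1 predicts. If someone leaves during baseline, the baseline mean is lowered and a real benefit can be hidden. Each participant is his or her own control, so there is no concurrent arm in which the distortion would cancel.

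The result on one of two primary outcomes therefore depends on an unstated rule, which could be settled after the data are seen. The antibiotic count under H3 goes into the same three-period model and inherits the gap.

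**Working it through.** **Inputs from the plan.** Mean of 6 UTIs per six months, SD 4, target reduction 1.25, alpha 0.025 per outcome, 120 recruited, 100 hoped for at the end. Going from 120 to 100 is 20 leavers, and 20% of 120 is 24, so both were used.

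**The plan's own figure.** Taking SD 4 as the SD of the within-person change and alpha as two-sided: 1.25/(4/√100) = 3.125, and Φ(3.125 - 2.241) = 0.81. The stated 81% is reproduced. The nominal chance of a false finding of benefit is half of 0.025, that is 1.25%.

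**Assumptions.** No true effect; leaving times uniform within the stated window; dropout unrelated to UTIs unless noted. Counts are gamma-Poisson with variance 16, in two settings:

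- 6 Poisson + 10 shared between periods: SD of change √(2×6) = 3.46.
- 6 Poisson + 8 shared + 2 person-by-period: SD of change √(2×8) = 4.

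**Hand check.** If n people enter a period and d leave during it, the mean raw count is 6 × [(n - d) + d/2]/n.

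- 24 leavers, even over months 6-18 (12 in the SMP period): 6 × (108 + 6)/120 = 5.70 against 6.00, a fall of 0.30.
- 24 leavers, even over 18 months (8 per period): baseline 6 × (112 + 4)/120 = 5.80; SMP 6 × (104 + 4)/112 = 5.79. Period means differ by only about 0.01. Among the 112 who enter the SMP period, however, the within-person fall is 8 × 3/112 = 0.21. The mixed model combines both sources of information and lands between them.

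**Simulated results, three-period random-intercept model with gender:**

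| Handling and dropout | SMP minus baseline (UTI) | False benefit (nominal 1.25%) |
|---|---|---|
| Part counts kept; 20-24 leavers, even over 18 months | -0.09 to -0.14 | about 2-3.5% |
| Part counts kept; 24 leavers, even over months 6-18 | about -0.30 | 7-9% |
| Part counts kept; 24 leavers, chance of leaving proportional to own UTI rate, even over 18 months | -0.16 to -0.20 | 3-5% |
| Part counts kept; 20-24 leavers, all in baseline | +0.19 to +0.30 | 0.1-0.3% |
| Part periods missing, or completers only | at most 0.01 in size | about 0.9-1.6% |

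Against the target, 0.09/1.25 = 7% and 0.14/1.25 = 11%.

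**Lower UTI rates.** At 1 UTI per period (the entry minimum of 2 a year), with 24 leavers spread evenly, the mixed-model shift is about -0.01 and false benefit is close to nominal.

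**With an offset for time observed.** Under dropout unrelated to UTIs the rate ratio is 1.00. False benefit is 1.4% (52 of 3,600 runs) for a negative-binomial mixed model and 1.1-1.9% for cluster-robust Poisson. When leaving is proportional to UTI rate, the SMP rate ratio is 0.99 for both (2.0% and 2.2%). For follow-up against baseline it is 0.99 (2.0%) and 0.97 (4.1%). The offset therefore does not fully correct dropout related to UTIs.

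**The case against.** The strongest reply is that the harm needs one particular reading. H1 refers to 100 participants and the power paragraph to a final N of 100, which may mean completers. The missing-data sentence may mean that a part period is a missing record. Under either, the mechanical bias is about zero when dropout is unrelated to UTIs. The words rate and incidence suggest that a rate may be intended. The plan also says the final form of the models is hard to predict, and Poisson is allowed, so an offset is not excluded. If UTIs come from medical records, as H3 permits for antibiotic use, ascertainment may not stop at withdrawal at all. Finally, with even dropout the effect partly cancels.

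All of that stands. It makes this an unspecified rule with a modest consequence, but it does not supply the rule.

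Three stronger inferences are tempting and are not supported:

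- *That the UTI result will be biased towards benefit.* The plan does not say part counts are kept, and dropout during baseline acts the other way.
- *That false benefit could reach 16-33%, with a shift of -0.49 to -0.61.* That needs every leaver to go during months 6-12. The plan speaks of dropout over the whole 18 months.
- *That even dropout costs up to 18% of the target.* That is the paired t-test figure (up to -0.22). The plan uses a t-test only for power; inference is by mixed model, where the range is 7-11%.

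**Conclusion.** The point holds as a conditional one and should be fixed. The UTI co-primary has no exposure term and no rule for part-observed periods. On the raw-count reading the planned model is biased, with a direction set by when people leave. For dropout spread evenly over 18 months the bias is modest: about -0.09 to -0.14 UTI, and false benefit of roughly two to three times nominal. It is larger if leaving is concentrated after month 6 or related to UTIs.

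These sizes rest on the plan's own mean of 6 and SD of 4, on assumed dropout timing and on gamma-Poisson counts. The documents do not settle which handling is intended, so confidence in the practical size is medium. The omission itself is plain in the text.

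**What to change.** Pre-specify for UTIs an overdispersion-robust count model that accounts for subject, either negative binomial with a subject effect or Poisson with cluster-robust errors. Keep gender and time as planned, and add log(time over which UTIs were ascertained) as offset. Keep part-observed periods and report the rate ratio. The evidence for preferring one of the two models is thin; either serves.

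Define exposure by how UTIs are learned of. If it is through weekly contact, leave out unobserved gaps as well as time after withdrawal, since the Phase II measurement section treats unanswered questionnaires as missed events. If records or self-report continue after withdrawal, let exposure continue too. Apply the same rule to the H3 antibiotic counts where ascertainment stops at withdrawal. Add a sensitivity analysis for dropout related to UTIs.

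Minimum alternative if the linear model is kept: state that part-observed periods are set to missing. This removes the mechanical bias but discards observed data.

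Cost: SAP wording and a record of when ascertainment was active. The Data and Safety Monitoring Plan already tracks withdrawal and loss to follow-up. The effect becomes a rate ratio, so the UTI power sentence must be restated on that scale. The case for the offset is bias control rather than power: in simulation the negative-binomial version gained only 1-2 points over a linear model with part periods missing.
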